5.2. Exclusion Criteria

A subject will not be eligible for inclusion in this study if any of the following criteria apply:

[1] Concomitant Medical Conditions

1. Significant concomitant medical conditions, defined as:
 - a. Historical or current evidence of clinically significant uncontrolled disease of any body system. Significant is defined as any disease that, in the opinion of the investigator or which would confound the interpretation of the study results if the disease/condition exacerbated during the study.
 - Significant renal impairment, which based on the opinion of the investigator, would preclude the subjects' participation in the study.
 - Current active liver or biliary disease (with the exception of Gilbert's syndrome or asymptomatic gallstones or otherwise stable chronic liver disease per investigator assessment).

NOTES:

 - Stable chronic liver disease should generally be defined by the absence of ascites, encephalopathy, coagulopathy, hypoalbuminaemia, oesophageal or gastric varices, or persistent jaundice, or cirrhosis.
 - Chronic stable hepatitis B and C (e.g., presence of hepatitis B surface antigen (HBsAg) or positive hepatitis C antibody test result at screening or within 3 months prior to first dose of study treatment) are acceptable if subject otherwise meets entry criteria.
 - b. A severe physical obstruction of the nose(e.g., deviated septum , nasal polyp or frequent bleeding of the nose that could affect the deposition of double blind intranasal study drug
 - c. Current or history of a Candida infection of the nose or oropharynx, shingles, chickenpox, measles, ocular herpes simplex.
 - d. Known hypersensitivity to corticosteroids or any excipients in the product.
 - e. Recent nasal septal surgery or nasal septal perforation
 - f. Subjects start, discontinue or change desensitization treatment within 30 days prior to Visit 1.
 - g. Bacterial or viral infection of the eyes or upper respiratory tract within two weeks of Visit 1 or during the screening period.
 - h. Asthma, with the exception of mild intermittent asthma [[Ruchi, 2009](#)]
 - i. Diagnosis of rhinitis medicamentosa, vasomotor AR or eosinophil rhinitis
2. Abnormal Laboratory Findings: A clinically significant laboratory abnormality

[1] Concomitant Medical Conditions

including Liver Function Tests at Visit 1 meeting the following criteria (as below and further defined in the study procedure manual):

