- ALT >2 x upper limit of normal (ULN) and bilirubin >1.5xULN (isolated bilirubin >1.5xULN is acceptable if bilirubin is fractionated and direct bilirubin <35%)

3. Abnormal ECG: Clinically significant abnormal ECG finding at Visit 1. Significant is defined as: QTc > 450 msec or QTc > 480 msec in subjects with Bundle Branch Block.

NOTES:

- The QTc is the QT interval corrected for heart rate according to Bazett's formula (QTcB), Fridericia's formula (QTcF), and/or another method, machine-read or manually over-read.
- The specific formula that will be used to determine eligibility and discontinuation for an individual subject should be determined prior to initiation of the study. In other words, several different formulae cannot be used to calculate the QTc for an individual subject and then the lowest QTc value used to include or discontinue the subject from the trial.
- For purposes of data analysis, QTcB, QTcF, another QT correction formula, or a composite of available values of QTc will be used as specified in the Reporting and Analysis Plan (RAP).

[2] Concomitant Medication

1. Use of prescription or over-the-counter medication that would significantly affect the course of AR, or interact with study drug (refer to [Table 1](#)), such as:

- Chronic use of concomitant medications such as tricyclic antidepressants, that would affect assessment of the effectiveness of the study drug
- Chronic use of long-acting beta₂-agonists (e.g., salmeterol)
- Potent Cytochrome P450 3A4 inhibitors (e.g., ritonavir, ketoconazole, itraconazole, clarithromycin, etc)
- Allergen immunotherapy for the treatment of allergies

2. Please refer to Section [6.9](#) for the list of concomitant medications permitted and prohibited during the study.

Table 1 Prohibited concomitant medications

Medications	Timeframe indicated relative to Visit 1

 1. Short-acting antihistamines, including ocular preparations and antihistamines contained in anti-cold medicine, insomnia or analgic. 2. Oral or inhaled anticholinergics 3. Oral or intranasal decongestants 4. Oral or intranasal antileukotrienes 5. Oral or inhaled long-acting beta2 agonists 6. Chinese traditional medicines that have potential effect to AR 7. Liquorice preparation 8. Medications that significantly inhibit the cytochrome P450 subfamily enzyme CYP3A4, including ritonavir and ketoconazole 	5 Days
tricyclic antidepressants	9 Days

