long-acting antihistamines(eg. desloratadine, fexofenadine, cetirizine and loratadine[taken as rescue medication])	10 Days
Intranasal antihistamines; or Intranasal or ocular cromolyh	16 Days
Intranasal corticosteroids	30 Days

 1. Inhaled, oral, intramuscular, intravenous, ocular and/or dermatological corticosteroid (with the exception of hydrocortisone cream/ointment, 1% or less) 2. Immunosuppressive medications 	60 Days
Subcutaneous omalizumab	5 months

[3] Subjects Will Travel More Than 48 Hours During the Study may Cause the Change of Allergen

[4] Investigators or Sub-investigators Consider that a Subject is Not Eligible

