7.5.6. Clinical Safety Laboratory Assessments

This study will use local laboratory except for liver event. All protocol required laboratory assessments, as defined in [Table 6](#), must be conducted in accordance with Protocol Time and Events Schedule. Reference ranges for all safety parameters will be provided by the local laboratory responsible for the assessments.

If additional non-protocol specified laboratory assessments are performed at the institution's local laboratory and result in a change in subject management or are considered clinically significant by the investigator (e.g., SAE or AE or dose modification) the results must be recorded in the CRF.

Refer to the SRM for appropriate processing and handling of samples to avoid duplicate and/or additional blood draws.

Haematology, clinical chemistry, urinalysis and additional parameters to be tested are listed in [Table 6](#).

Table 6 Protocol Required Safety Laboratory Assessments

Laboratory Assessments	Parameters			
Haematology	Platelet Count	Red blood cells (RBC) Indices:	White Blood Cells (WBC) count with Differential :	
	RBC Count	MCV	Neutrophils	
	Hemoglobin	MCH	Lymphocytes	
	Hematocrit		Monocytes	
			Eosinophils	
			Basophils	
Clinical Chemistry ¹	Blood urea nitrogen (BUN/UREA)	Potassium	AST (Serum glutamic-oxaloacetic transaminase (SGOT))	Total and direct bilirubin
	Creatinine	Sodium	ALT (Serum glutamic pyruvic transaminase (SGPT))	Total Protein
	Glucose	Calcium	Alkaline phosphatase	Albumin
Routine Urinalysis ²	
 • Specific gravity • pH, glucose, protein, blood and ketones • Microscopic examination (if blood or protein is abnormal) 			

NOTES :
 
 1. Details of Liver Chemistry Stopping Criteria and Required Actions and Follow-Up Assessments after liver stopping or monitoring event are given in Section 5.5.2 and Appendix 2 2. Local urine testing will be standard for the protocol unless serum testing is required by local regulation or ethics committee. 				

All laboratory tests with values that are considered clinically significantly abnormal during participation in the study or within 4 days after the last dose of study treatment should be repeated until the values return to normal or baseline. If such values do not return to normal within a period judged reasonable by the investigator, the etiology should be identified and the sponsor notified.

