12.2. Appendix 2: Liver Safety Required Actions and Follow up Assessments

Liver chemistry stopping criteria and required follow up assessments

Liver Chemistry Stopping Criteria - Liver Stopping Event	
ALT-absolute	ALT \geq 8xULN
ALT Increase	ALT \geq 5xULN but <8xULN persists for \geq 2 weeks ALT \geq 3xULN but <5xULN persists for \geq 4 weeks
Bilirubin^{1, 2}	ALT \geq 3xULN and bilirubin \geq 2xULN (>35% direct bilirubin)
International Normalised ratio (INR)²	ALT \geq 3xULN and INR>1.5, if INR measured
Cannot Monitor	ALT \geq 5xULN but <8xULN and cannot be monitored weekly for \geq 2 weeks ALT \geq 3xULN but <5xULN and cannot be monitored weekly for \geq 4 weeks
Symptomatic³	ALT \geq 3xULN associated with symptoms (new or worsening) believed to be related to liver injury or hypersensitivity
Required Actions and Follow up Assessments following ANY Liver Stopping Event	
Actions	Follow Up Assessments

 Immediately discontinue study treatment Report the event to GSK within 24 hours Complete the liver event CRF and complete an SAE data collection tool if the event also meets the criteria for an SAE² Perform liver event follow up assessments Monitor the subject until liver chemistries resolve, stabilize, or return to within baseline (see MONITORING below) Do not restart/rechallenge subject with study treatment unless allowed per protocol and GSK Medical Governance approval is 	
 Viral hepatitis serology⁴ Only in those with underlying chronic hepatitis B at study entry (identified by positive hepatitis B surface antigen(HBsAg)) quantitative hepatitis B DNA and hepatitis delta antibody⁵. Blood sample for pharmacokinetic (PK) analysis, obtained within 72 hours after last dose⁶ Serum creatine phosphokinase (CPK) and lactate dehydrogenase (LDH). Fractionate bilirubin, if total bilirubin\geq2xULN

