
ALT \geq5xULN and <8xULN and bilirubin <2xULN without symptoms believed to be related to liver injury or hypersensitivity, and who can be monitored weekly for 2 weeks.
 
OR
 
ALT \geq3xULN and <5xULN and bilirubin <2xULN without symptoms believed to be related to liver injury or hypersensitivity, and who can be monitored weekly for 4 weeks.
	
 • Notify the GSK medical monitor within 24 hours of learning of the abnormality to discuss subject safety. • Subject can continue study treatment • Subject must return weekly for repeat liver chemistries (ALT, AST, alkaline phosphatase, bilirubin) until they resolve, stabilise or return to within baseline • If at any time subject meets the liver chemistry stopping criteria, proceed as described above • If ALT decreases from ALT \geq5xULN and <8xULN to \geq3xULN but <5xULN, continue to monitor liver chemistries weekly. • If, after 4 weeks of monitoring, ALT <3xULN and bilirubin <2xULN, monitor subjects twice monthly until liver chemistries normalize or return to within baseline.

References

12.3. Appendix 3: Definition of and Procedures for Recording, Evaluating, Follow-Up and Reporting of Adverse Events

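### The numeric liver exclusion joins ALT and bilirubin with *and*, which leaves its own bracket without function and lets isolated ALT above 2xULN pass

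*Protocol*

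**What the plan says.** Protocol 5.2, under Abnormal Laboratory Findings, excludes a clinically significant laboratory abnormality, "including Liver Function Tests at Visit 1 meeting the following criteria (as below and further defined in the study procedure manual"). One bullet follows: "ALT >2 x upper limit of normal (ULN) and bilirubin >1.5xULN". Its bracket adds that "isolated bilirubin >1.5xULN is acceptable if bilirubin is fractionated and direct bilirubin <35" per cent.

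This is the only numeric liver limit for entry in either document. Neither amendment described in Protocol Appendix 4 touches it, and the SAP does not restate it.

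Three other provisions bear on entry:

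- Protocol 5.2 excludes active liver or biliary disease, but excepts Gilbert's syndrome and "asymptomatic gallstones or otherwise stable chronic liver disease per investigator assessment". Chronic stable hepatitis B and C are also permitted if the other entry criteria are met.
- The last exclusion is a general one: "Investigators or Sub-investigators Consider that a Subject is Not Eligible".
- Protocol Appendix 2 sets the on-treatment liver rules. ALT of 8xULN or more is a stopping event, with the action "Immediately discontinue study treatment". ALT from 3 to below 8xULN allows continued treatment with weekly chemistry, provided bilirubin is below 2xULN, there are no liver or hypersensitivity symptoms, and weekly monitoring is feasible.

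**The concern.** The connector and the bracket point to different entry rules. Under *and*, a child must exceed both limits to be excluded, so a child with isolated raised bilirubin is never excluded and needs no exception. The bracket is useful only if bilirubin above 1.5xULN can exclude by itself.

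A site could well take *and* literally, because Appendix 2 uses the same word between ALT and bilirubin for conditions that must hold together, as in "<5xULN and bilirubin <2xULN without symptoms believed to be related to liver injury or hypersensitivity". Section 5 of the protocol allows no deviation from the entry criteria and section 5.4 rules out re-screening. Two centres reading the bullet differently would therefore make different and final decisions on the same results. SAP Appendix 9 expects about 12 centres.

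The stake is participant safety and uniform eligibility. Clinical laboratory tests are scheduled only at Visit 1 and at Visit 5 or early withdrawal. Unless Appendix 2 is applied to the Visit 1 value, a child who enters with raised ALT has no scheduled chemistry until Day 29.

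**Working it through.** The plan states no figure to reproduce. The check is one of logic.

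**Inputs.** The ALT limit (>2xULN), the bilirubin limit (>1.5xULN) and the direct fraction (<35%) are from Protocol 5.2. The action levels of 3, 5 and 8xULN are from Protocol Appendix 2.

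**Step 1: does the bracket do anything?** Let A = ALT >2xULN, B = bilirubin >1.5xULN, F = bilirubin fractionated with direct <35%. The bracket exempts a child when B holds, A does not, and F holds. The table shows whether the child is excluded.

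| A | B | F | *and* | *and* + bracket | *or* | *or* + bracket |
|---|---|---|---|---|---|---|
| no | no | no | no | no | no | no |
| no | no | yes | no | no | no | no |
| no | yes | no | no | no | yes | yes |
| no | yes | yes | no | no | yes | **no** |
| yes | no | no | no | no | yes | yes |
| yes | no | yes | no | no | yes | yes |
| yes | yes | no | yes | yes | yes | yes |
| yes | yes | yes | yes | yes | yes | yes |

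Under *and* the bracket changes 0 of 8 rows. Under *or* it changes 1 of 8, which is exactly the case it describes. The literal rule and the separate limits (both with the bracket) differ in 3 of 8 rows: isolated ALT (two rows) and isolated bilirubin without a low direct fraction (one row).

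**Step 2: what the difference means at particular values.** These eight Visit 1 profiles are assumed for illustration and are not trial data. The last column shows what Appendix 2 would require if it were applied to the Visit 1 ALT. The weekly-check entries assume no symptoms and feasible weekly monitoring.

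| ALT (xULN) | Bilirubin (xULN) | Direct | Literal *and* | Separate limits | Appendix 2 action on ALT |
|---|---|---|---|---|---|
| 1.0 | 1.0 | 20% | passes | passes | none |
| 2.5 | 1.0 | 20% | passes | excluded | none |
| 4 | 1.0 | 20% | passes | excluded | weekly checks; stop if it persists 4 weeks or more |
| 7 | 1.0 | 20% | passes | excluded | weekly checks; stop if it persists 2 weeks or more |
| 9 | 1.0 | 20% | passes | excluded | stop at once |
| 1.0 | 1.8 | 20% | passes | passes | none |
| 1.0 | 1.8 | 50% | passes | excluded | none |
| 2.5 | 1.8 | 50% | excluded | excluded | none |

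The literal rule excludes 1 profile, separate limits exclude 6, and the two disagree on 6 - 1 = 5 (every profile excluded by the literal rule is also excluded by separate limits). The seventh profile fails the bracket's own condition and still passes the literal rule.

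**The case against.** The strongest reply is that the bullet is not the whole criterion. The lead-in excludes any clinically significant laboratory abnormality, and the liver bullet can be read as one specified instance. On that reading, isolated ALT of 4, 7 or 9xULN judged clinically significant is excluded by the same item. The bracket then has a role: it marks mild indirect hyperbilirubinaemia as acceptable, in line with the Gilbert's syndrome exception. The bracket also hints that separate limits were meant, and the study procedure manual may say so outright.

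Part of this stands. The general wording, the active liver disease exclusion, investigator discretion and the manual may each keep such a child out, so enrolment is possible but not assured. But the first three are judgements without an ALT cut-off, and the manual was not supplied. The bullet exists to supply the number, and its number fails if followed as written. Reading the bracket as a carve-out from the general wording does not repair the numeric rule.

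Three further points are fair:

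- Appendix 2 governs children on treatment, so the comparison with it shows mismatched thresholds and not a formal contradiction.
- The count of 5 of 8 depends on the profiles chosen; four of the five are isolated ALT at different levels. It illustrates the difference and estimates nothing.
- Protocol 7.5.6 requires laboratory values judged clinically significantly abnormal during participation to be repeated until they return to normal or baseline. That could cover ALT between 2 and 3xULN, where Appendix 2 requires nothing, but it too depends on judgement.

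**Conclusion.** The concern holds. As written, the numeric liver exclusion operates only when both limits are exceeded. Its bracket exempts nobody from that rule, and isolated ALT above 2xULN passes it at any level. The conclusion about the wording rests on the current text of Protocol 5.2 alone and is firm. How sites applied it cannot be known without the study procedure manual.

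The practical size is small. The documents give no frequency of raised liver tests, few children are likely to be affected, and the risk assessment in Protocol 4.5.1 lists no hepatic risk. The sample size and the primary analysis are unaffected. This is a correction worth considering because it concerns an eligibility threshold in a paediatric trial, where following the text literally gives the wrong result.

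**What to change.** Reword the bullet so that each limit excludes separately: ALT >2xULN; *or* bilirubin >1.5xULN, with the existing bracket retained and attached to the bilirubin limb only. Bring the study procedure manual into line with that wording.

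The cost is one connector in one bullet and at most a few more screen failures; there would be none if sites already apply separate limits. No extra sample is needed: ALT and "Total and direct bilirubin" are already in Table 6 of Protocol 7.5.6, and the Time and Events Table schedules clinical laboratory tests at Visit 1.

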5.3. Randomisation Criteria

[1] At Visit 2, the Subject must continue to meet the inclusion/exclusion criteria above. In addition the subject must meet the following criteria:

- a. On the morning of Visit 2, subjects must have nasal or/and ocular symptoms.
- b. Average of the last 8 rTNSS assessments (4 AM assessments, 4 PM assessments) over the consecutive four 24-hours periods prior to randomization must be ≥ 6 . This includes the AM assessment on the morning of Visit 2.
- c. Average of the 8 reflective nasal symptom assessments for congestion (4 AM assessments, 4 PM assessments) over the consecutive four 24-hour periods prior to randomization must be ≥ 2 . This includes the AM assessment on the morning of Visit 2.

5.4. Screening/Baseline/Run-in Failures

Subjects who fail to meet the eligibility requirements at Visit 1 are considered a screen failure. Subjects who fail to meet the eligibility requirements at Visit 2 are considered a run-in failure. Subjects who are screen or run-in failures should not be re-screened.

Data for screening/Run-in failures will be collected in source documentation at the site and will be transmitted to GSK. The following information will be collected in the case report form (CRF) for subjects who are screen/Run-in failures:

- Date of screening Visit
- Subject number
- Date of ICF signature
- Demographic information including race, age and gender
- Reason for screen/run-in failure
- SAE information

5.5. Withdrawal/Stopping Criteria

5.5.1. Withdrawal criteria

5.5.1.1. Subject Withdrawal from the Investigational Product

Premature discontinuation of the study drug will be defined as discontinuation of the study drug for more than or equal 2 consecutive days before the end of the treatment period. Subjects who discontinue administration of study drug prematurely will be withdrawn from the study.

5.5.1.2. Subject Withdrawal from the Study

A subject who takes double-blinded study drug but withdraws prior to Visit 5 will be defined as withdrawn early. Subjects who withdrew early will not be replaced.

Subject withdrew from the study was required and Early Withdrawal procedures must be performed, when:

- A subject is significantly non-compliant with the requirements of the protocol.
- A subject has an adverse event that would, in the investigator's judgment, make continued participation in the study an unacceptable risk.
- Lost to follow-up
- The treatment blind is broken for a subject (by other than GSK GCSP personnel), or
- GSK discontinues the study.
- Female subjects experience menarchal during study.

The following actions must be taken in relation to a subject who fails to attend the clinic for a required study visit:

- The site must attempt to contact the subject (or subject parents/guardian) and re-schedule the missed visit as soon as possible.
- The site must counsel the subject on the importance of maintaining the assigned visit schedule and ascertain whether or not the subject wishes to and/or should continue in the study.
- In cases where the subject is deemed 'lost to follow up', the investigator must make every effort to regain contact with the subject (where possible, 3 telephone calls and if necessary a certified letter to the subject's last known mailing address or local equivalent methods). These contact attempts should be documented in the subject's medical record.
- Should the subject continue to be unreachable, only then will he/she be considered to have withdrawn from the study with a primary reason of "Lost to Follow-up".

A subject may withdraw from study treatment at any time at his/her own request, or may be withdrawn at any time at the discretion of the investigator for safety, behavioural or administrative reasons. If a subject withdraws from the study, he/she may request destruction of any samples taken, and the investigator must document this in the site study records:

- Review all information recorded on diary cards, including rTNSS, rTOSS, study medication administration, rescue medication use., any medical conditions or concomitant medications
- Investigators must complete subjects' nasal examination by anterior rhinoscopy and these examined results must be recorded on patient notes.
- Conduct adverse event assessment

- Physical examination, vital signs and nasal examination
- 12-lead Electrocardiogram
- Double-blind study drug collection
- Clinical laboratory tests

These data should be recorded in the CRF, as appropriate, as they comprised an essential evaluation that should be done prior to discharging any subject from the study.

Subjects who have discontinued IP in the study should be encouraged to return to the clinic as soon as possible to complete the IP Discontinuation Visit assessments and to complete the safety follow-up contact 3 to 7 days following the subject's last dose. If a subject is prematurely discontinued during a regularly scheduled visit, that visit will become the Early Withdrawal visit.

[figure not shown]
Any clinically significant adverse event, laboratory test, nasal examination, Electrocardiogram (ECG) finding, or clinically significant unfavorable change observed during the Early Withdrawal Visit necessitated that the subject be followed or treated until satisfactory resolution occurred.

In the event that a subject was prematurely discontinued from the study at any time due to an AE or SAE, the procedures stated in protocol must be followed.

[figure not shown]
